**Eligibility Checklist**

Yes	No	N/A	Inclusion Criteria (All responses must be YES in order to enter study)	Eligibility Confirmation (registrar)
			1. Does the patient have histologically proven myelodysplastic syndrome having failed at least one line of previous therapy?	
			2. Does the patient have an ECOG performance status of $\leq 3$ ?	
			3. Is the patient 18 years of age or older?	
			4. Does the patient have an estimated survival of $> 2$ months?	
			5. Has the patient recovered from the acute, non-hematological, non-infectious toxicities of any prior treatment with cytotoxic drugs, radiotherapy or other anti-cancer modalities? Patients with persisting, non-hematologic, non-infectious toxicities from prior treatment $\leq$ Grade 2 are eligible, but must be documented as such.	
			6. If the patient is a woman of child-bearing potential (i.e., pre-menopausal or not surgically sterile), does she agree to use accepted contraceptive methods (abstinence, intrauterine device [IUD], oral contraceptive or double barrier device) during the study, and agree to have a negative serum or urine pregnancy test within 1 week prior to treatment initiation?	
			7. If the patient is a fertile man, does he agree to practice effective contraceptive methods during the study, unless documentation of infertility exists?	
			8. Does the patient have documentation of the following laboratory values? 
 
• aspartate aminotransferase [AST/SGOT] <math>\leq 3x</math> upper normal limit [UNL]
 
• alanine aminotransferase [ALT/SGPT] <math>\leq 3x</math> UNL (<math>\leq 5x</math> UNL if liver metastases present)
 
• bilirubin <math>\leq 1.5x</math> UNL
 
• serum creatinine <math>\leq 1.5</math> mg/dL or 133 <math>\mu</math>mol/L
 
• Albumin <math>> 2.0</math> g/dL or <math>> 20</math> g/L.
 
	
			9. Is the patient mentally competent, able to understand and willing to sign an IRB-approved written informed consent document?	
			10. Does the patient have access via a central line (e.g., portacath)?	

Yes	No	N/A	Exclusion Criteria (All responses must be NO in order to enter study)	Eligibility Confirmation (registrar)
			1. Has the patient received radiotherapy, surgery, treatment with cytotoxic agents (except CPI-613), treatment with biologic agents, immunotherapy, or any other anti-cancer therapy of any kind, or any other standard or investigational treatment for their cancer, or any other investigational agent for any indication, within the past 2 weeks prior to initiation of CPI-613 treatment?	
			2. Has the patient received a chemotherapy regimen with stem cell support in the previous 6 months?	
			3. Does the patient have a serious medical illness, such as significant cardiac disease (e.g. symptomatic congestive heart failure, unstable angina pectoris, coronary artery disease, myocardial infarction within the past 3	

CCCWFU # 29113

**Eligibility Checklist**

		months, uncontrolled cardiac arrhythmia, pericardial disease or New York Heart Association Class III or IV), or severe debilitating pulmonary disease, that would potentially increase patients' risk for toxicity.	
		4. Does the patient have any active uncontrolled bleeding or bleeding diathesis?	
		 5. Is the patient a pregnant woman, or a woman of child-bearing potential who is not using reliable means of contraception?	
		 6. Is the patient a lactating female?	
		 7. Is the patient a fertile man who is unwilling to practice contraceptive methods during the study period?	
		 8. Is the patient's life expectancy less than 2 months?	
		 9. Does the patient have an unrelated central nervous system (CNS) or epidural tumor?	
		 10. Does the patient have any condition or abnormality which may, in the opinion of the investigator, compromise his or her safety?	
		 11. Is the patient unwilling or unable to follow protocol requirements?	
		 12. Does the patient have a history of additional risk factors for torsade de pointes (e.g., heart failure, hypokalemia, family history of Long QT Syndrome)?	
		 13. Does the patient have evidence of active infection, or serious infection within the past month?	
		 14. Does the patient have known HIV infection?	
		 15. Does the patient require immediate palliative treatment of any kind, including surgery?	
		 16. Does the patient have a prior history of illicit drug addiction?	
		 17. Does the patient have large and recurrent pleural or peritoneal effusions requiring frequent drainage (e.g., weekly)?	
		 18. Does the patient have any amount of clinically significant pericardial effusion?	

This subject is  eligible /  ineligible for participation in this study.

ORIS Assigned PID: \_\_\_\_\_

Signature of research professional confirming eligibility: \_\_\_\_\_ Date: \_\_\_\_\_

Signature of Treating Physician: \_\_\_\_\_ Date: \_\_\_\_\_

Signature of Principal Investigator\*\*: \_\_\_\_\_ Date: \_\_\_\_\_

\* Examples of source documents include clinic note, pathology report, laboratory results, etc. When listing the source, specifically state which document in the medical record was used to assess eligibility. Also include the date on the document. Example: "Pathology report, 01/01/14" or "Clinic note, 01/01/14"

\*\*Principal Investigator signature can be obtained following registration if needed

*Please send source documentation with Eligibility Form.*

Comprehensive Cancer Center of Wake Forest University (CCCWFU)  
A Pilot Study of CPI-613 in Patients with Myelodysplastic Syndrome Who Have Failed Previous Therapy  
CCCWFU #29113

**CCCWFU # 29113**

**Protocol Registration Form**

**DEMOGRAPHICS**

Patient: Last Name: \_\_\_\_\_

First Name: \_\_\_\_\_

MRN: \_\_\_\_\_

DOB (mm/dd/yy): \_\_\_\_\_ / \_\_\_\_\_ / \_\_\_\_\_

SEX: \_\_\_\_\_

Male

Ethnicity (choose one):  Hispanic

Female

Non-Hispanic

Race (choose all that apply):

WHITE  BLACK  
 PACIFIC ISLANDER

ASIAN

NATIVE AMERICAN

Height: \_\_\_\_\_.\_\_\_\_ inches

Weight: \_\_\_\_\_.\_\_\_\_ lbs.(actual)

Surface Area: \_\_\_\_\_.\_\_\_\_ m^2

Zip Code: \_\_\_\_\_

Primary Diagnosis: \_\_\_\_\_

Date of Diagnosis: \_\_\_\_ / \_\_\_\_ / \_\_\_\_

**PROTOCOL INFORMATION**

Date of Registration: \_\_\_\_\_ / \_\_\_\_\_ / \_\_\_\_\_

MD Name (last) : \_\_\_\_\_

Date protocol treatment started: \_\_\_\_\_ / \_\_\_\_\_ / \_\_\_\_\_

Informed written consent:

YES  NO

(consent must be signed prior to registration)

Date Consent Signed: \_\_\_\_\_ / \_\_\_\_\_ / \_\_\_\_\_

PID # (to be assigned by ORIS): \_\_\_\_\_

*Protocol Registrar can be contact by calling [contact] between 8:30 AM and 4:00 PM, Monday – Friday.*

*Completed Eligibility Checklist and Protocol Registration Form must be hand delivered, faxed or e-mailed to the registrar at [name] or [[contact]](mailto:[contact]).*

## Appendix B: STRC SAE REPORTING GUIDELINES

### Mandatory STRC SAE Reporting Requirements – Revised 6/05/2012

Safety and Toxicity Review Committee (STRC; previously known as CROC) Serious Adverse Event (SAE) Notification SOP	Date: 8/17/2016
---	------------------------

### Mandatory STRC SAE Reporting Requirements

This document describes STRC reporting and use of the electronic submission form that is submitted **for unexpected grade 4 and any grade 5 (death during protocol intervention) SAEs on WFBCCC Institutional interventional trial patients**. There are multiple entities that require reporting of SAEs. Each entity has different rules for what is reported, and how it is reported.

Rules used by other entities (Institutional Review Board (IRB), AdEERS, MedWatch, etc.) should NOT be used to evaluate whether an event should be reported to STRC. Only the rules for reporting described in this document should be considered.

As defined in the NCI Data Table 4 reporting guidelines, **WFBCCC Institutional Interventional studies covered by these reporting requirements are defined as: In-house, internally reviewed trials, including those collaborative studies conducted with industry sponsorship in which the center is a primary contributor to the design, implementation, and monitoring of the trial, or participation in a multi-site trial initiated by an institutional investigator at another center**. Institutional trials are almost always authored by a researcher here at WFBCCC. Institutional protocols are labeled NCI Code="I" for Institutional on the protocol screen in ORIS. Cooperative group protocols are **not** considered Institutional, but Research Base trials **are** classified as Institutional.

The STRC is responsible for reviewing SAEs for WFBCCC Institutional Interventional studies, as defined above. STRC currently requires that unexpected grade 4 and all grade 5 SAEs on these trials be reported to the STRC for review. All Clinical Protocol and Data Management (CPDM) staff members assisting a PI in documenting and reporting an SAE that qualifies for STRC reporting are responsible for informing a clinical member of the STRC by phone (or in-person), followed by informing the entire committee via the required email notification.

**THESE REPORTING REQUIREMENTS APPLY TO any faculty or staff member on the study team for a WFBCCC Institutional Interventional trial. Once an event is observed, it is the responsibility of the person who observed the event to be sure that it is reported.**

### What is considered an SAE under this mandatory procedure?

Any **unexpected grade 4 event and all grade 5 events** (death during protocol intervention) should be reported. These events should be reported if they occur while a patient is on study treatment or if they occur within 30 days of last study treatment (even if patient begins a new treatment during the 30 days). This window of 30 days should be the standard window to be used in all protocols unless a specific scientific rationale is presented to suggest that a shorter

window can be used to identify events. In addition, if it is not clear whether the Grade 4 is unexpected it should be reported.

**Table 1: Summary of STRC Reporting Requirements for Institutional Pilot, Phase 1, Phase 2 and Phase 3 Interventional Trials**

	ADVERSE EVENT					
	Grade 1, Grade 2, Grade 3		Grade 4		Grade 5	
	Unexpected	Expected	Unexpected	Expected	Unexpected	Expected
Unrelated	Not Required	Not Required	REPORT TO STRC	Not Required	REPORT TO STRC	REPORT TO STRC
Unlikely	Not Required	Not Required	REPORT TO STRC	Not Required	REPORT TO STRC	REPORT TO STRC
Possible	Not Required	Not Required	REPORT TO STRC	Not Required	REPORT TO STRC	REPORT TO STRC
Probable	Not Required	Not Required	REPORT TO STRC	Not Required	REPORT TO STRC	REPORT TO STRC
Definite	Not Required	Not Required	REPORT TO STRC	Not Required	REPORT TO STRC	REPORT TO STRC

STRC reporting may not be appropriate for specific expected adverse events for protocols. In those situations the adverse events that will not require STRC reporting **must be specified in the text of the approved protocol.**

**STRC notification responsibilities of the person handling the reporting/documenting of the SAE:**

1. Make a phone call (or speak in person) to the appropriate clinical member of the STRC as listed below (page if necessary)—see note 2 below
2. Submit the STRC Notification Form WITHIN 24 HOURS of first knowledge of the event. This form is found at either the ORIS main menu page or by going to <http://ccc.wfubmc.edu/oris/strc.aspx>.

This will ensure that all persons that need to be made aware of the event (i.e., study team members and STRC members) will be notified; remember to file a copy of your confirmation. (Form instructions will walk you through the required fields, consult the help page for further instructions.)

3. Ensure that you document that the appropriate person(s) on the STRC has been contacted. This documentation is placed on the STRC Notification form described above.
4. Follow up with/update the clinical member(s) of STRC regarding any new developments or information obtained during the course of the SAE investigation and reporting process.

**Elements to complete the electronic STRC form:**

**Please use 'reply to All' when responding with one of these terms: Definite, Probable, Possible, Unlikely, or Unrelated**

1. Patient ID (ORIS PID)
2. Patient Name
3. Patient MR#

4. WFBCCC(ORIS) Study Number
5. Title
6. PI Name
7. PI Contact Number
8. PI Comments
9. STRC Clinician notified by Phone
10. Notified Date
11. Notified Time
12. STRC Clinician Comments
13. Category [This is the Grade – Either Unexpected Grade 4 or Grade 5 should be entered]
14. Additional Information (IRB Reporting)(after discussion with PI or STRC Clinician)
  - i. Is This Event Related to Protocol Treatment?
  - ii. Is Suspension of the Protocol Needed?
  - iii. Any Changes to Consent or Protocol Needed?
  - iv. Was Nature or Severity of Event Unexpected?
15. Date of the event.
16. Brief description (include brief clinical history relevant to this event, including therapies believed related to event).
17. Date of Last Dose before event
18. Relevant tests/labs.
19. Other Relevant Treatment Information
20. Other Comments/Notes (include regimen of chemo and dates the patient received them if known).
21. Cc (email) (include treating Physician; separate email list with comma ",")
22. Your Name
23. Your Email
24. Confirm Your Email

**Definition of Unavailable:**

As a general guideline if the first clinician that is contacted does not respond to the phone call or page within a reasonable amount of time, then initiate contact with their backup. Give the backup a reasonable amount of time to respond to a phone call or page before contacting another member. This is a general guideline. You must use your best judgment as a clinical research professional given the time of day, severity of the SAE, and other circumstances as to when it is appropriate to contact backup clinicians. If the event occurs near the end of day, then leave messages (voice or email) as appropriate and proceed with submitting your STRC notification form. The important criteria is that you have taken reasonable steps to notify and document that you have initiated some type of contact to one or more of the clinical members of STRC.

**STRC CLINICAN RESPONSIBILITY:**

It is the responsibility of the STRC clinician to review all reported events, evaluate the events as they are reported; and communicate a response to the Investigator, event reporter and the members of STRC. The review will include but not be limited to the information reported; there may be times when additional information is needed in order for an assessment to be made and further communication directly with the investigator may be warranted. STRC reserves the right to agree with the investigator's assessment if STRC does not agree with the investigator. STRC reserves the right to suspend the trial pending further investigation.

Is there any immediate danger or harm that could be present for a future patient based on the information provided in the STRC report – and if so an immediate suspension of enrollment should take place.

**AMENDMENTS TO PREVIOUS REPORTS**

If you are not able to supply all pertinent information with the initial submission, once the additional information is available **do not submit a new report**. Go to the original email that was received by STRC and others "reply to all" and entitle your email "**Amendment** for (list date of event and patient ID) this will avoid duplications of the same event. List the additional information which you are reporting.

**Acronyms and Definitions**

**STRC**-Safety and Toxicity Review Committee

**SAE**-Serious Adverse Event

**IRB**-Institutional Review Board

**WFBCCC**-Comprehensive Cancer Center Wake Forest University

**ORIS**-Oncology Research Information System

**NCI**-National Cancer Institute

**CPDM**-Clinical Protocol and Data Management

**Interventional Trials**-Therapeutic Level 1 and Level 2 trials

**Therapeutic Level 1**-A cancer treatment protocol aimed at directly treating/curing the patient's cancer.

**Therapeutic Level 2**-A therapeutic protocol not cancer treatment involves clinical activity to treat symptoms, improve the patient's quality of life, or prevent cancer.

Comprehensive Cancer Center of Wake Forest University (CCCFWU)  
A Pilot Study of CPI-613 in Patients with Myelodysplastic Syndrome Who Have Failed Previous Therapy  
CCCFWU #29113

## Appendix C – CCCWFU ADVERSE EVENT LOG

## WFBCCC Adverse Event (AE) Log

PI: \_\_\_\_\_

PID: \_\_\_\_\_

MRN: \_\_\_\_\_

**Cycle Start Date:** \_\_\_\_\_

**Cycle End Date:** \_\_\_\_\_

**Cycle #:** \_\_\_\_\_

\*Serious Adverse Event: Hospitalization; Disability; Birth Defect; Life-threatening; Death.

CTCAE Version 4 - [http://evs.nci.nih.gov/ftp1/CTCAE/CTCAE\\_4.03\\_2010-06-14\\_QuickReference\\_8.5x11.pdf](http://evs.nci.nih.gov/ftp1/CTCAE/CTCAE_4.03_2010-06-14_QuickReference_8.5x11.pdf)

## Appendix D – Withdrawal of Participation Form

ORIS PID \_\_\_\_\_

Date Completed \_\_\_\_ / \_\_\_\_ / \_\_\_\_

Name of person completing form \_\_\_\_\_

Did the subject meet eligibility criteria for study enrollment? Yes  No

### Reasons for withdrawal: (Check all that apply and provide additional information)

- Patient exhibited progression of disease
- Unacceptable toxicity from CPI-613 in spite of dose reduction
- Patient withdrawal of consent
  - For just the primary intervention (CPI-613 administration only)
  - For all components of the research study (including follow up in the medical record)
- Investigator's discretion to withdraw patient from the study because continued participation in the study is not in the patient's best interest
- Undercurrent illness: a condition, injury, or disease unrelated to the intended disease for which the study is investigating, that renders continuing the treatment unsafe or regular follow-up impossible
- General or specific changes in the patient's condition that renders the patient ineligible for further investigational treatment
- Non-compliance with investigational treatment, protocol-required evaluations or follow-up visits
- Termination of the clinical trial by the clinical sponsor

COMMENTS: \_\_\_\_\_  
\_\_\_\_\_  
\_\_\_\_\_

## Appendix E – Data Collection Form for Bone Marrow Exam

Study ID: \_\_\_\_\_

Date: \_\_\_\_ / \_\_\_\_ / \_\_\_\_

Most recent cycle completed: Baseline  Cycle 3  Cycle 6   
Other  \_\_\_\_\_

Bone Marrow Exam:

Morphology: \_\_\_\_\_

Cellularity: \_\_\_\_\_

Karyotype (cytogenetics and FISH as applicable):  
\_\_\_\_\_  
\_\_\_\_\_

Molecular markers: \_\_\_\_\_

% of bone marrow myoblasts: \_\_\_\_\_ %

Revised IPSS Classification:  Very Low  Low  Intermediate  High  Very High

## Appendix F – Data Collection Form for Number of Transfusions

Study ID: \_\_\_\_\_

Date form completed: \_\_\_\_ / \_\_\_\_ / \_\_\_\_

Time point of assessment:    Baseline     Cycle 2     Cycle 4     Cycle 6   
                                  Cycle 9     Cycle 12     Other \_\_\_\_\_

Frequency of transfusion is defined as the number of transfusions received during the previous 8 weeks. The baseline assessment should reflect the number of transfusions received in the 8 weeks prior to enrollment. On-treatment assessments should be performed at the end of every 2 treatment cycles.

Number of RBC transfusions during period (circle): 0 1 2 3 4 5 6 7 8 9 10

Date range of assessment period: \_\_\_\_ / \_\_\_\_ / \_\_\_\_ to \_\_\_\_ / \_\_\_\_ / \_\_\_\_

Number of platelet transfusions during period (circle): 0 1 2 3 4 5 6 7 8 9 10

Date range of assessment period: \_\_\_\_ / \_\_\_\_ / \_\_\_\_ to \_\_\_\_ / \_\_\_\_ / \_\_\_\_

## Appendix G –Pre-Study Data Collection Form

**ORIS PID:** \_\_\_\_\_ **DATE COMPLETED:** (mm/dd/yy): \_\_\_\_ / \_\_\_\_ / \_\_\_\_

**The following are required prior to registration:**

**CURRENT DISEASE STATUS AT REGISTRATION:** \_\_\_\_\_

(1ST relapse, 2nd relapse, 3rd relapse, refractory etc., including allo or auto bone marrow transplant)

Prior Therapies/ Protocol # if applicable	Start / End Date of Prior Therapy	Best Response (CR, PR, Treatment Failure)	Date of Best Response	Date of Relapse	Duration of Best Response (in Months)
#1 _____	____ / ____	_____	_____	_____	_____
#2 _____	____ / ____	_____	_____	_____	_____
#3 _____	____ / ____	_____	_____	_____	_____
#4 _____	____ / ____	_____	_____	_____	_____
#5 _____	____ / ____	_____	_____	_____	_____
#6 _____	____ / ____	_____	_____	_____	_____

**COMMENT:** \_\_\_\_\_

**Date of original cancer diagnosis:** \_\_\_\_ / \_\_\_\_ / \_\_\_\_

**Date of 1st Remission:** \_\_\_\_ / \_\_\_\_ / \_\_\_\_

**Date of 1st Relapse:** \_\_\_\_ / \_\_\_\_ / \_\_\_\_

**Date of 2nd Relapse:** \_\_\_\_ / \_\_\_\_ / \_\_\_\_

### ECOG Performance Status:

- Score 0** – Fully active, able to carry on all pre-disease performance without restriction
- Score 1** - Restricted in physically strenuous activity but ambulatory and able to carry out work of a light or sedentary nature, e.g., light house work, office work
- Score 2** - Ambulatory and capable of all selfcare but unable to carry out any work activities. Up and about more than 50% of waking hours
- Score 3** - Capable of only limited selfcare, confined to bed or chair more than 50% of waking hours
- Score 4** - Completely disabled. Cannot carry on any selfcare. Totally confined to bed or chair

### CYTOGENETICS:

#### Cytogenetics at Diagnosis:

**Date of Cytogenetics Report:** \_\_\_\_ / \_\_\_\_ / \_\_\_\_

**Risk Category:**  Good  Intermediate  Poor

\*Enter descriptive text from Cytogenetic Report (3 categories) into REDCap database on Pre-Study Data Collection Form.

Revised IPSS Classification:  Very Low  Low  Intermediate  High  Very High

## Appendix H – Response Criteria

**Table 3. Proposed modified International Working Group response criteria for altering natural history of MDS**

Category	Response criteria (responses must last at least 4 wk)
Complete remission	
Bone marrow: <math>\leq 5\%</math> myeloblasts with normal maturation of all cell lines*
 
Persistent dysplasia will be noted†
 
Peripheral blood‡
 
 
Hgb <math>\geq 11</math> g/dL
 
Platelets <math>\geq 100 \times 10^9/L</math>
 
Neutrophils <math>\geq 1.0 \times 10^9/L</math>†
 
Blasts 0%
 

Partial remission	
All CR criteria if abnormal before treatment except:
 
Bone marrow blasts decreased by <math>\geq 50\%</math> over pretreatment but still <math>> 5\%</math>
 
Cellularity and morphology not relevant

Marrow CR†	
Bone marrow: <math>\leq 5\%</math> myeloblasts and decrease by <math>\geq 50\%</math> over pretreatment†
 
Peripheral blood: if HI responses, they will be noted in addition to marrow CR†

Stable disease	
Failure to achieve at least PR, but no evidence of progression for <math>> 8</math> wks

Failure	
Death during treatment or disease progression characterized by worsening of cytopenias, increase in percentage of bone marrow blasts, or progression to a more advanced MDS FAB subtype than pretreatment

Relapse after CR or PR	
At least 1 of the following:
 
 
Return to pretreatment bone marrow blast percentage
 
Decrement of <math>\geq 50\%</math> from maximum remission/response levels in granulocytes or platelets
 
Reduction in Hgb concentration by <math>\geq 1.5</math> g/dL or transfusion dependence
 

Cytogenetic response	
Complete
 
 
Disappearance of the chromosomal abnormality without appearance of new ones
 
 
Partial
 
 
At least 50% reduction of the chromosomal abnormality
 

Disease progression	
For patients with:
 
 
Less than 5% blasts: <math>\geq 50\%</math> increase in blasts to <math>> 5\%</math> blasts
 
5%-10% blasts: <math>\geq 50\%</math> increase to <math>> 10\%</math> blasts
 
10%-20% blasts: <math>\geq 50\%</math> increase to <math>> 20\%</math> blasts
 
20%-30% blasts: <math>\geq 50\%</math> increase to <math>> 30\%</math> blasts
 
 
Any of the following:
 
 
At least 50% decrement from maximum remission/response in granulocytes or platelets
 
Reduction in Hgb by <math>\geq 2</math> g/dL
 
Transfusion dependence
 

Survival	
Endpoints:
 
 
Overall: death from any cause
 
Event free: failure or death from any cause
 
PFS: disease progression or death from MDS
 
DFS: time to relapse
 
Cause-specific death: death related to MDS
 

Deletions to IWG response criteria are not shown.

To convert hemoglobin from grams per deciliter to grams per liter, multiply grams per deciliter by 10.

MDS indicates myelodysplastic syndromes; Hgb, hemoglobin; CR, complete remission; HI, hematologic improvement; PR, partial remission; FAB, French-American-British; AML, acute myeloid leukemia; PFS, progression-free survival; DFS, disease-free survival.

\*Dysplastic changes should consider the normal range of dysplastic changes (modification).

†Modification to IWG response criteria.

‡In some circumstances, protocol therapy may require the initiation of further treatment (eg, consolidation, maintenance) before the 4-week period. Such patients can be included in the response category into which they fit at the time the therapy is started. Transient cytopenias during repeated chemotherapy courses should not be considered as interrupting durability of response, as long as they recover to the improved counts of the previous course.

Continued on next page

Comprehensive Cancer Center of Wake Forest University (CCCFWU)  
A Pilot Study of CPI-613 in Patients with Myelodysplastic Syndrome Who Have Failed Previous Therapy  
CCCFWU #29113

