### 2.2 Outcome Measures

The primary outcome measure is to evaluate the response rate (RR) of CPI-613 in these patients. Response rate is defined as the combined rate of complete remission (CR), marrow CR, partial remission (PR), or stable disease (SD) as described by Cheson, et al. (2006).

The secondary outcome measures are:

- Safety
- Progression-free-survival (PFS)
- Overall survival (OS)
- Changes in the frequency of blood transfusion
- Hematologic improvement (HI; as defined by Cheson et al . [2006])

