### 5.1.3 Assessment of Anti-Cancer Activities

Tumor response will be assessed based on RR, PFS, and OS (as described by Cheson et al. 2006), as well as changes in the frequency of transfusion from baseline. RR and PFS, derived from hematology and bone marrow exam. Hematology will be assessed at baseline, during week 4 of every 2 treatment cycles until cycle 6, and then every 3 treatment cycles thereafter until disease progression. Bone marrow will be assessed at baseline, cycle 3 and 6 and then at the discretion of the physician or if peripheral blood criteria for a complete remission are met (ie ANC>1000, Platelets >100k and freedom from blood transfusions) thereafter until disease progression.

Baseline frequency should be recorded as the number of transfusions received during the 8 weeks prior to enrollment. Once patients have started protocol treatment, transfusion

frequency should be assessed at the end of every 2 treatment cycles.

Survival will be assessed during the study and will be monitored by treating physician contact after the patients are taken off the trial.

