### Proposed Analyses

The analyses for this protocol will be primarily descriptive. With a sample size of 20 treated at MTD, we do not expect to see statistically significant effects for the outcomes of interest, however this data will provide useful preliminary data on the overall safety and efficacy of CPI-613 and provide useful data to predict the variability and likely effect sizes for these outcomes.

For the primary outcome, we will present the proportion (along with a 95% confidence interval) of patients who respond. Response rate (RR) is defined as the combined rate of CR, marrow CR, PR, or SD as described by Cheson, et al. (2006). Response criteria are shown in Appendix G. In addition, we will determine the number of patients who achieve HI, and a reduction in transfusion requirements. For the time-to-event outcomes, we will estimate survival curves for OS and PFS using Kaplan-Meier techniques. In addition, we will estimate the 6 month and 1-year OS and PFS rates for these participants. We will also examine toxicities by looking at each toxicity identified earlier in the protocol by grade.

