## **10.0 Data Management and Reporting Schedule**

Tumor response will be assessed based on RR, PFS, and OS (as described by Cheson et al. 2006), as well

Comprehensive Cancer Center of Wake Forest University (CCCFWFU)  
A Pilot Study of CPI-613 in Patients with Myelodysplastic Syndrome Who Have Failed Previous Therapy  
CCCFWFU #29113

as changes in the frequency of transfusion from baseline.

RR and PFS, derived from hematology and bone marrow exam, will be assessed at the following specified time points:

- Baseline (hematology and bone marrow)
- Hematology: week 4 of every 2 treatment cycles until cycle 6 and then every 3 treatment cycles thereafter (i.e., cycle 9, cycle 12, cycle 15, etc) until evidence of disease progression.
- Bone marrow week 4 of cycles 3 and 6, and then at the discretion of the physician or if peripheral blood criteria for a complete remission are met (ie ANC>1000, Platelets >100k and freedom from blood transfusions) thereafter until disease progression

Bone marrow exam results should be documented at each specified time point using the data collection form in Appendix E, and then input into the corresponding REDCap database.

Transfusion frequency should be documented at each specified time point using the data collection form in Appendix F, and then input into the corresponding REDCap database.

Response form (Appendix I) should be completed for each specified time point.

	Data Collection Forms	Due By	Database
Pre-Study / Registration	Signed Consent Registration Form	At time of registration At time of registration	ORIS ORIS
On-Study	Adverse event log (Appendix C) Withdrawal of participation form (Appendix D) Bone marrow exam form (Appendix E) Transfusion data form (Appendix F) Response form (Appendix I)	Within one week Within one week Within one week Within one week Within one week	ORIS REDCap REDCap REDCap REDCap

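### PFS counts only progression or MDS death, so plain Kaplan-Meier censors other deaths and reported PFS can exceed the share alive and progression-free

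*Combined protocol and SAP*

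**What the plan says.** PFS is listed as a secondary outcome in section 2.2 without a definition. Section 5.1.3 states that "Tumor response will be assessed based on RR, PFS, and OS", following the 2006 International Working Group criteria, and section 10.0 repeats this. Those criteria are reproduced in Appendix H. The survival lines of Table 3 there hold the only PFS definition in the documents: "PFS: disease progression or death from MDS". The same table counts every death, whatever its cause, for overall survival and for event-free survival. Event-free survival is not an outcome of this trial.

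For the analysis, section 9.0 says "we will estimate survival curves for OS and PFS using Kaplan-Meier techniques" and "we will estimate the 6 month and 1-year OS and PFS rates for these participants". It gives no censoring rule, no competing-risk method and no rule for deaths unrelated to MDS. The only other statement on deriving PFS is in section 10.0, with a near-identical one in section 5.1.3: "RR and PFS, derived from hematology and bone marrow exam, will be assessed at the following specified time points". It names laboratory and marrow data and does not mention death.

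**The concern.** Most readers will take a 6-month or 1-year PFS rate as the share of patients alive without progression at that time. Under this definition it need not be. A patient who dies of a non-MDS cause before progressing leaves the risk set as censored, and Kaplan-Meier then treats that patient as someone who could still have progressed later. The error runs in the favourable direction only. It matters because section 9.0 says the trial will "provide useful data to predict the variability and likely effect sizes for these outcomes", so the PFS figures may be carried into the planning of later studies.

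The definition also needs each death to be attributed to MDS or not, and the documents give no rule for that. Section 1.1 presents infection and bleeding as consequences of MDS, so such deaths could be classed either way. The attribution scale in section 8.1 and the safety committee (STRC) form in Appendix B ask about relation to study treatment, not to MDS. The withdrawal and response forms (Appendices D and I) show no cause-of-death field.

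**Working it through.** **The plan's own figure.** The plan states no PFS figure. Its one computed design figure is the precision of the response rate, 0.22 with 20 patients. The Wald half-width at 50% reproduces it: 1.96 × √(0.25/20) = 0.219. It is used below only for scale.

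**Inputs from the documents.** N = 20, single arm (section 6.1). PFS event: progression or MDS death (Appendix H). Method: Kaplan-Meier, read at 6 and 12 months (section 9.0). Follow-up: 5 years or until death (section 6.3), so non-MDS deaths before progression can be observed.

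**Assumed inputs, because the documents give none.** Constant hazards; median time to progression or MDS death 6 months, varied from 4 to 12; non-MDS death hazard equal to r = 0.10, 0.25 or 0.50 times the hazard λ of progression or MDS death.

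**Step 1: direction.** With the same risk sets, counting fewer event types can only raise the product-limit estimate. So PFS with non-MDS deaths censored is at or above PFS with them counted. With no other censoring, the latter is exactly the proportion alive and progression-free.

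**Step 2: size under the assumptions.** λ = ln 2 / 6 per month. Reported PFS = exp(−λt). Alive and progression-free = exp(−λ(1+r)t).

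| r | 6 mo: reported | 6 mo: true | Excess (points) | 12 mo: reported | 12 mo: true | Excess (points) |
|---|---|---|---|---|---|---|
| 0.10 | 50.0% | 46.7% | 3.3 | 25.0% | 21.8% | 3.2 |
| 0.25 | 50.0% | 42.0% | 8.0 | 25.0% | 17.7% | 7.3 |
| 0.50 | 50.0% | 35.4% | 14.6 | 25.0% | 12.5% | 12.5 |

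Over medians of 4 to 12 months the excess is 2.4 to 14.8 points at 6 months and 2.3 to 14.8 at 12. The maximum for r = 0.50 is that of S − S^1.5, which is 4/27 = 14.8 points at S = 4/9.

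**Step 3: expected number of such deaths.** By month 6, 20 × [r/(1+r)] × (1 − true proportion) = 0.97, 2.32 and 4.31. At r = 0.10 the chance of none by month 6 is (1 − 0.0485)^20 = 0.37, and the bias at that landmark is then zero.

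**Step 4: counts.** Suppose that by 12 months there are 10 PFS events and 4 non-MDS deaths before progression, leaving 6 of 20 (30.0%) alive and progression-free. With the deaths falling after the 2nd, 4th, 7th and 10th events, Kaplan-Meier gives (18/20) × (15/17) × (11/14) × (7/10) = 43.7%. It is 37.5% if all four deaths come first and 50.0% if all come last. With a single such death after the 5th of 10 events it is (15/20) × (9/14) = 48.2% against 9/20 = 45.0%.

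**Step 5: one death.** With Kaplan-Meier value S and n at risk just before it, one non-MDS death creates an excess of S/n at that time over the curve that counts it.

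- No other censoring: S = n/20, so 1/20 = 5.0 points, shrinking with later events.
- Five early censorings and no events: 1/15 = 6.7 points.
- Nine events, then five censorings: 0.55/6 = 9.2 points (55.0% against 45.8%).

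Such censoring is possible, because Appendix D allows withdrawal from all study components.

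**Step 6: can PFS exceed OS?** Yes, but with no other censoring only if non-MDS first deaths outnumber progressed patients still alive. Example: 3 non-MDS deaths, then 9 PFS events, 8 of those 9 dead by month 6. PFS = 8/17 = 47.1%, OS = 9/20 = 45.0%, alive and progression-free = 8/20 = 40.0%. If 2 of the 9 are still alive, OS = 10/20 = 50.0% and the reversal disappears.

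**The case against.** The strongest reply is that this is a choice of endpoint, not an error. The line belongs to a published consensus table that separates overall, event-free, progression-free and cause-specific survival, and its PFS is the disease-specific member of that set. That is fair as to the table. It does not cover pairing the definition with plain Kaplan-Meier, no handling of competing deaths and no attribution rule, then reporting the result as a PFS rate.

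The same table makes any death during treatment a Failure, so one patient can be a Failure on the response form and censored for PFS. The two categories serve different purposes, so this is an awkwardness rather than a contradiction.

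Several limits on importance stand:

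- Section 9.0 says "The analyses for this protocol will be primarily descriptive". No decision uses PFS, and OS at the same landmarks counts every death.
- Progression is defined broadly and would often precede death. Section 3.2 excludes serious cardiac or pulmonary illness and recent serious infection. If infection and bleeding deaths are attributed to MDS, the problem shrinks further.
- Against that, section 3.1 admits any risk group, and section 1.1 notes that most patients are older and that lower-risk patients may live for years.
- Every illustrated excess is below the 22-point half-width. A confidence interval describes random error, however, and does not correct a bias in one direction.

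A further point stands as a separate gap. Disease assessments are tied to treatment cycles, so progression after treatment stops may go unrecorded. Any-cause PFS does not cure that. The present definition has the same weakness for MDS deaths, so it is no reason to keep it.

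**Conclusion.** The concern holds. Followed as written, the plan censors non-MDS deaths before progression, and reported PFS is at or above the proportion alive and progression-free. The wording and the direction of the bias are certain. Its size is not, and rests entirely on assumed constant hazards and an assumed share of non-MDS deaths: roughly 2 to 15 points over the ranges shown, and zero if no such death occurs. The 50% case needs about 4 such deaths in 20 by month 6, and nothing in the documents supports or rules that out. PFS exceeding OS is possible but needs a particular pattern of events. The primary response rate is untouched. This is worth fixing because the repair is cheap and the estimates are the product of a descriptive pilot, but it does not threaten the trial's main conclusion.

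**What to change.** In sections 2.2 and 9.0, state that the PFS event is disease progression or death from any cause, whichever comes first, and that this overrides the PFS line in Appendix H, Table 3. Leave the reproduced published table unedited.

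The cost is one sentence in each section. The data are those OS already needs, since patients are followed until death or for 5 years, and the unstated step of attributing deaths to MDS is no longer needed. The price is a small departure from the published criteria, less direct comparability with studies that use them verbatim, and a somewhat lower PFS.

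If the MDS-death version is also wanted for comparability, report it as the cumulative incidence of progression or MDS death with non-MDS death as a competing event, and add a written attribution rule and a cause-of-death field. That costs more. STRC reports cover deaths on treatment or within 30 days, with a narrative and relation to treatment, but not later deaths or relation to MDS. The fields of the Appendix C log are not visible in the copy reviewed, so whether it could help cannot be judged.
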